Aim 1: Establish the feasibility and acceptability of Caring Cards for Veteran card makers and recipients (i.e., 70% average group attendance, > 75% average satisfaction with group participation and card receipt, and 70% average follow-up response). Establish feasibility and acceptability for optional meetup groups (i.e., 70% average meetup group attendance [feasibility] and > 75% average satisfaction with meetup groups [acceptability]).

Aim 2: Evaluate pre/post changes in thwarted belongingness and perceived burdensomeness among card-makers and recipients.

Aim 3: Evaluate pre/post changes in social connectedness and suicide risk among card makers and recipients.

Section 7 - Background and Significance

7) Provide a succinct discussion of relevant background information to justify performing the proposed study.

Veteran suicide is an epidemic; from 2005-2016, suicide rates have risen 26% despite increased prevention efforts. Suicide prevention is VA's highest priority. Efforts to expand and develop innovative services are required to address this ever-growing problem. Thwarted belongingness and perceived burdensomeness are potent transdiagnostic social risk factors for suicide. Unfortunately, few interventions have directly targeted these constructs to reduce suicide risk. The overarching goal of this project is to refine and evaluate Caring Cards, an innovative peer-centered intervention that aims to reduce suicide risk by promoting social recovery among Veterans. Inspired by caring contacts for suicide prevention and the recovery model, Caring Cards employs a novel approach to social recovery by leveraging Veterans' lived experience with mental health conditions. In Caring Cards, Veterans compose messages of hope and unity by handmaking one-of-a-kind cards in outpatient groups. These cards are then sent to their anonymous peers who identified to be at elevated risk for suicide.

In a recent pilot study conducted by [name] and colleagues (IRB #H190032), preliminary data indicate Caring Cards is highly feasible and acceptable to both Veteran card makers and recipients. These data also suggest Caring Cards benefits both Veteran card makers and

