Optional Meet-Up Groups (card makers and recipients): All study participants will be invited to attend one or more monthly, 120-minute optional, unstructured meetup groups at the VASDHS facilitated by a therapist. A total of four meet-up groups will be offered throughout the study's duration. Again, if COVID-19 precautions are in effect and these groups cannot meet in person, they will be invited to meet via WebEx. Meet-up groups will begin with an introduction to the purpose of the group (i.e., the facilitator will explain that this is an opportunity for the card makers and recipients to meet one another) followed by a review of basic group rules (i.e., limits of confidentiality will be reviewed, group members will be informed that they are free to come and go as they please, meaning they can arrive later than the designated start time and leave earlier than the end time, and the facilitator will be available if anyone has any questions or concerns). The facilitator will remind meet-up group attendees that if they are having thoughts of suicide or homicide, they should speak directly to them. If group is conducted virtually, the Veteran may ask the facilitator to call them after the group has concluded. If suicide is reported, the group's facilitator will further assess their risk by completing a C-SSRS; if the Veteran's C-SSRS is positive, the facilitator will contact the PI for further risk assessment and Safety Planning.

Follow-up Assessments: All follow-up assessments will be collected in-person or via remote methods described above by the study coordinator.

Follow-up assessment battery includes: Beck Scale for Suicidal Ideation (BSS), C-SSRS "Since Last Contact," Interpersonal Needs Questionnaire (INQ-15), NIH Toolbox Adult Social Relationship Scales, and Intervention Satisfaction Questionnaire (developed by PI).

Card makers: Veterans are expected to participate in the Caring Cards groups for six months. Follow-up assessments will be collected within one month of the last group meeting. If a card maker drops out prior to the group's end date, follow-up will be collected within one month the last group meeting they attended. **Card recipients:** Follow-up assessments will be collected within one month after the delivery of the final card. If a card recipient drops out prior to this, follow-up will be collected within one month after the last card they received.

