Feasibility & Acceptability: Feasibility for card makers will be assessed by the proportion of enrolled Veterans who attend all scheduled Caring Cards groups. Feasibility for recipients will be assessed by the ratio of cards sent and received. For all participants, feasibility will be measured by the proportion of Veterans 1) referred for screening, 2) determined eligible, 3) enrolled /completed baseline, and 4) complete follow-up assessments. Feasibility of the optional meet-up groups will also be evaluated based on average attendance. Acceptability for all participants will be assessed by the Intervention Satisfaction Questionnaire, a measure that will be developed by the research team to assesses Veterans' satisfaction with their participation in the Caring Cards and meet-up groups (if attended), as well as asks for feedback about Caring Cards and assesses reasons for study dropout or non-attendance to meet-up groups.

Participant Compensation: Participants will be paid a total of \$120 to complete the baseline and follow-up assessment (\$60 each). No recruitment will take place year two. We would like to pay participants \$120 at baseline, or \$60 at each assessment (baseline and follow-up).

Fidelity: For groups, Caring Cards is a manualized intervention and the facilitator (trained by the PI) will run the groups. The PI will review audiotapes of treatment delivery using a fidelity rating scale, and feedback will be shared in weekly supervision. To assess fidelity for sending cards, quantity, timing, and receipt of the cards will be recorded by the study's research assistant. The study coordinator will monitor the accuracy of this record.

In our original protocol we were approved to use VA-approved audio recording devices to record the groups to ensure fidelity. Given that some groups are likely to take place via telehealth, we would like to amend our protocol to include recording groups via WebEx. VA WebEx has a recording features and for all telehealth groups, we propose to use this feature to record the sessions. The recordings of these WebEx groups will be stored via within the VA WebEx account used to facilitate the group. These recordings will be stored via password protection behind VA firewall and encrypted VA-specific WebEx account (i.e., veteransaffairs.webex.com). Only study personnel will have access to these recordings.

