12.15.21 Amendment Meet-up Groups for Former Participants: We plan to invite former study participants - i.e., those who have completed thier follow-up assessments, to participate in our optional meet-up groups. As noted above, we plan to hold 120-minute optional, unstructured meetup groups at the VASDHS (Rio or LJ clinics) facilitated by a therapist/research personnel. One to four meet-up groups may be offered throughout the study's duration. Meet-up groups will begin with an introduction to the purpose of the group (i.e., the facilitator will explain that this is an opportunity for the card makers and recipients to meet one another) followed by a review of basic group rules (i.e., limits of confidentiality will be reviewed, group members will be informed that they are free to come and go as they please, meaning they can arrive later than the designated start time and leave earlier than the end time, and the facilitator will be available if anyone has any questions or concerns). The facilitator will remind meet-up group attendees that if they are having thoughts of suicide or homicide, they should speak directly to them. If group is conducted virtually, the Veteran may ask the facilitator to call them after the group has concluded. If suicide is reported, the group's facilitator will further assess their risk by completing a C-SSRS; if the Veteran's C-SSRS is positive, the facilitator will contact the PI for further risk assessment and Safety Planning.

Former participants who agreed at consent to be re-contacted will be called via telephone and invited to join these optional meet-up groups. See telephone script. In addition feasibility and acceptability data will be collected from those who join. Specifically, we will record attendance (feasibility) and one to two weeks following the final meet-up group offered, former participants will be called and invited to answer follow-up questions based on their participation the meet-up groups (acceptability). See script.

Section 9.8 Questionnaires & Surveys

9.8) Provide the name and a reference for questionnaires/surveys that are standard or identify them here and attach a copy of the questionnaire/survey. Questionnaires or surveys that are not clinical standard references must be uploaded. Reference the help link for additional information related to surveys administered to VA personnel and approved platforms for web-based surveys.

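### Could the 70% meet-up attendance benchmark be met automatically because the amendment collects data from those who join and allows a single group?

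*Protocol*

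**What the plan says.** Section 6, Aim 1 sets the meet-up feasibility benchmark as "70% average meetup group attendance [feasibility", beside a satisfaction benchmark for acceptability. Section 9, under Feasibility & Acceptability, repeats the measure without adding a divisor: "Feasibility of the optional meet-up groups will also be evaluated based on average attendance".

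Section 9, under Optional Meet-Up Groups, sets out the offer: "All study participants will be invited to attend one or more monthly, 120-minute optional, unstructured meetup groups", and "A total of four meet-up groups will be offered".

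The 12.15.21 amendment, also in Section 9, extends the meet-ups to people who have finished follow-up. It says "One to four meet-up groups may be offered", that "Former participants who agreed at consent to be re-contacted will be called via telephone" to be invited, and that "feasibility and acceptability data will be collected from those who join". It then specifies that "we will record attendance (feasibility" and that acceptability will be asked about by telephone after the last group.

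**The concern.** A feasibility benchmark is useful only if it can be missed. Read literally, the amendment gathers attendance from people who join, which suggests a proportion calculated among attenders. If a single meet-up is held, everyone in that divisor has attended every session on offer, so the figure is 100% whether four people came or forty. The 70% mark would then say nothing about whether invited Veterans come, which is the open question for a type of group that Section 7 describes as not yet examined.

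Two further features add to the worry. The text offering four groups to all participants was left beside amendment text allowing one to four groups for former participants. And the database contents listed in Section 27.4 include meet-up attendance but do not mention who was invited.

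**Working it through.** The 70% is a stated threshold with no derivation, so there is no figure to reproduce. The check is whether it can be missed under each divisor the text allows.

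**Inputs.** Benchmark 70% (Section 6). Groups held, k: four (Section 9, Optional Meet-Up Groups) or one to four (12.15.21 amendment). Planned sample 80, made up of 30 card makers and 50 recipients (Section 9). The number who agreed to re-contact is not given, so the counts of people invited or accepting below are assumptions.

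**Formula.** Average attendance = total attendances / (people in the divisor × k).

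**1. Divisor: people who attended at least once.** With n such people, total attendances are at least n, so the average is at least n/(n × k) = 1/k.

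| Groups held | Lowest possible average | Can 70% be missed? |
|---|---|---|
| 1 | 100% | No |
| 2 | 50% | Yes |
| 3 | 33.3% | Yes |
| 4 | 25% | Yes |

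The result is automatic in the first row only.

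**2. Divisor: people invited.** Take one group and assume all 80 planned participants are invited. Then 70% needs 0.70 × 80 = 56 attenders (21 of 30 makers plus 35 of 50 recipients). With 16 attenders the figure is 16/80 = 20%, against 16/16 = 100% among attenders. If 4 people come and 20, 40 or 80 are assumed invited, it is 20%, 10% or 5%. The benchmark can clearly be missed.

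**3. Divisor: people who accepted the telephone invitation.** The amendment's preceding sentence has former participants telephoned and invited to join, so joining can mean saying yes on that call. People who accept and do not come then count against attendance, even with one group: 10 of an assumed 20 is 50%. With 20 accepting, the binomial probability that fewer than 14 come is 0.94, 0.39 or 0.002 for assumed show rates of 50%, 70% or 90%.

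**What the wording settles.** The amendment sentence says who supplies data; it does not say what attendance is divided by. Its next sentence says only that attendance is recorded. The measure in Feasibility & Acceptability has no restriction to joiners, and nothing in the amendment says it redefines the Aim 1 measure.

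**Whether prescribing invitations as divisor would help.** Participants are invited to one or more optional groups. Someone who attends one of four has done what was asked, yet scores 1/4 = 25%. If all 80 attended exactly one of four, uptake would be 80/80 = 100% while average attendance over invitations would be 80/(80 × 4) = 25%, a failure. Writing in that divisor would amount to choosing a stricter criterion.

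**The case for a change.** The strongest opposing case is that Section 9 gives a divisor for its other feasibility measures (enrolled Veterans for the card makers, cards sent for the recipients) and none for the meet-ups. The amendment's telephone questions concern participation in the meet-ups, which favours reading joiners as attenders. The satisfaction questionnaire does ask why people did not attend, but it belongs to the follow-up battery, which people invited under the amendment have already completed. And no analysis plan can recover invitation counts that were never kept.

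Much of this stands: the divisor is unstated, and the questionnaire does not fill the gap for former participants. The loss of invitation counts is not shown, however. Under the Optional Meet-Up Groups text everyone enrolled is invited, so the enrolment list gives the count. Under the amendment, the pool is those who agreed at consent to re-contact, and invitations are made by scripted telephone call. The script and consent pages are not available here, so what they record cannot be judged. Section 27.4 answers a storage question and need not list every item kept.

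The mismatch between four groups and one to four is real but clerical. This form repeatedly adds amendment text beside the text it modifies, and four lies within one to four.

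**Conclusion.** The arithmetic behind the worry is right for one case, but that case depends on three conditions the protocol does not impose: attenders as divisor, joining meaning attending, and exactly one group held. Drop any one and 70% can be missed.

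What is left is a missing detail in a descriptive proportion, of the kind an analyst ordinarily settles when defining the measure. Reporting the number of groups held, the number invited and the number attending each lets a reader calculate any of the versions above; a bare 100% from one session would mislead nobody who saw those counts. Prescribing one divisor in the protocol brings no clear gain, because the obvious candidate penalises people who attend as invited. The card-making groups, card receipt and follow-up response are judged separately and are unaffected.

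This conclusion assumes that the enrolment list, re-contact answers and call records allow invitees to be counted. The counts of 20, 40 and 80 invited, 20 accepting and the show rates are illustrative and do not come from the protocol. No change to the plan follows.

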We would like to amend our approach by including recruiting participants via their providers. Specifically, we would like to approach VA healthcare providers/clinics (e.g., Primary Care Mental Health Integration, Center of Recovery Education, Mood Clinic, PTSD Clinic), with information about the study, asking them to share this information with their Veterans.

Providers will share study information verbally and/or via study flyer (see below) with Veterans during their standard clinical interactions. If a Veteran is interested in learning more about the study, providers will ask their permission to have our study personnel reach out to them to discuss screening/enrollment. Providers will alert study personnel to interested Veterans via encrypted VA email or adding them as additional signers to Veterans' CPRS progress notes.

Last, providers will inform Veterans that they can directly reach out to our study personnel if they are interested in participating. Contact information for personnel will be provided on our study flyer described below.

To facilitate recruitment via providers, we would like to share a study flyer with providers/clinics so they can distribute to their Veterans. Please see attached for a draft of our flyers – one for card makers and one for card recipients. Moreover, we have an information flyer for providers, which we have included as well.

Screening: As noted above, Veterans with inactive and active HRFs will be introduced to the study via a letter and subsequent phone call. The study coordinator will screen potential participants based on the following inclusion/exclusion criteria.

Inclusion criteria for card-makers: (1) VASDHS Veteran with an inactive high-risk flag, (2) 18 years of age or older, (3) access to transportation to attend the group, and (4) decisional capacity.

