Inclusion criteria card recipients: (1) VASDHS Veteran with an active high-risk flag, (2) 18 years of age or older, and (3) decisional capacity. *Exclusion criteria for card makers and recipients:* (1) the absence of a mailing address, working phone number, and email address, (2) inability to read and write in English, (3) previous or current experience as either card maker or recipient, and (4) currently employed by the VA San Diego. If COVID-19 precautions are in effect, Veterans will also be screened for access to reliable computer, tablet, or smartphone with camera and internet access, as well as the willingness to participate in this study remotely. Participants' decisional capacity for informed consent in order to meet eligibility for this study will be assessed during consent (separate from screening call) via the University of California San Diego Brief Assessment of Capacity to Consent (UBACC) will be collected by the study coordinator.

Given that we will likely be conducting at least some of our groups via telehealth, we would like to amend our inclusion criteria for card makers by distinguishing between in person groups vs. telehealth groups for criterion #3, which will be amended to (3) access to transportation to attend the group (if being held in person).

We would also like to amend our exclusion criteria for card makers by adding (5) if participating in group via telehealth, the absence of access to reliable computer, tablet, or smartphone with camera and internet access.

Enrollment- Consent and Baseline Assessment: Following the screening procedures outlined above, Veterans will be invited to participate as either a card maker or recipient (depending on their HRF status). Consent and baseline assessments will be completed either via phone, VA Video Connect (VVC), WebEx, or in-person. If consent is obtained via phone or VVC, or WebEx, we will adhere to current approved guidelines (i.e., use My Health-e-Vet, using MS Azure, have Veteran send signed consent form via email, have Veterans fax, or have the study coordinator take a screen shot of the signed consent during their VVC or WebEx session).

Following consent, Veterans will complete a baseline assessment battery that consists of the following questionnaires: Beck Scale for Suicidal Ideation (BSS), Columbia-Suicide Severity Rating Scale (C-SSRS), Interpersonal Needs Questionnaire (INQ-15), and NIH Toolbox Adult Social Relationship Scales.

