If a Veteran is conservated, the study coordinator will obtain their conservator's consent for study enrollment, as well as the assent of the conserved Veteran.

Caring Cards Groups (Veteran card makers with inactive HRFs): Our study will include three groups, each with 10 Veterans; they will meet separately for 120 minutes once per week at the VASDHS for six months. If groups are unable to take place in-person due to COVID-19 precautions, groups will take place using the VA-approved virtual platform, WebEx. Groups will be facilitated by a post-doctoral or intern-level therapist supervised by the PI, who is a licensed clinical psychologist. If groups are unable to meet in-person, art supplies and cards will be mailed to the group members at their mailing address. If groups take place remotely, this may increase recruitment; however, due to the scope of this pilot project, enrollment will be capped at 10 Veterans per group (a total of 30 card makers). Group members will be assessed for suicide risk at enrollment and follow-up. In addition, the groups' facilitator will remind Veterans at the start of each group to please let them know before the end of group if they are experiencing any thoughts of suicide or homicide. If group is conducted virtually, the Veteran may ask the facilitator to call them after the group has concluded. If suicide is reported, the group's facilitator will further assess their risk by completing a C-SSRS; if the Veteran's C-SSRS is positive, the facilitator will contact the PI for further risk assessment and Safety Planning.

Sending Caring Cards (Veteran card recipients with active HRFs): A total of six cards, one per month, for six months will be mailed. Veterans recruited from psychiatric inpatient care will be mailed a card within the week following their discharge; cards will be sent on a monthly basis thereafter. This is consistent with post-discharge caring contacts recommendations. The study coordinator will contact Veterans via phone two weeks after the card was sent to confirm they received it. Because card-recipients are receiving regular contact by VA Suicide Prevention Coordinators and will receive formal suicide risk assessment at enrollment and follow-up, they will not be directly assessed for suicide risk following the mailing of each card.

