For all study prospective participants, after they have been screened, determined to be eligible to participate, and agree to participate, a member of the research team (e.g., study coordinator) will obtain Veterans' consent to participate in the study and assess decisional capacity for informed consent at this time. Consent may be obtained in person (at VA San Diego La Jolla or Rio clinic locations), via phone, WebEx, or VA Video Connect. As previously mentioned, if consent is obtained remotely, we will adhere to current approved guidelines (i.e., use My Health-e-Vet, using MS Azure, have Veteran send signed consent form via email, have Veterans fax, or have the study coordinator take a screen shot of the signed consent during their VVC or WebEx session).

For inpatient prospects, the study coordinator will consult with the PI and/or the Veteran's treating inpatient teams to determine the appropriate timing of approaching Veteran on the unit. If appropriate, the study coordinator will conduct screening on the unit, and if agreeable to participate, consent and baseline assessments may be completed prior to or following discharge.

If a Veteran is conservated, the study coordinator will obtain their conservator's consent for study enrollment, as well as the assent of the conservated Veteran.

Due to the persistence of the COVID-19 pandemic, we plan to enroll participants via telehealth. In our original protocol, we received approval to obtain consents via telehealth. Per our original protocol, "If consent is obtained via phone or VVC, or WebEx, we will adhere to current approved guidelines (i.e., use My Health-e-Vet, using MS Azure, have Veteran send signed consent form via email, have Veterans fax, or have the study coordinator take a screen shot of the signed consent during their VVC or WebEx session)." We would like to amend this approach to include obtaining consent via the WebEx File Transfer feature. Below are the procedures that will be taken to obtain consent via this method.

Webex Consent Appointment (for participant on laptop/computer)

1. Go to your Personal Room by visiting its URL on your computer's browser outside of your remote connection/CAG and click Join Meeting.
 - a. <https://veteransaffairs.webex.com/meet/first.lastname>
2. Go to your Personal Room by visiting its URL on the browser inside your remote connection (CAG).
 3. Allow your outside connection entrance into the meeting
 4. In the WebEx app inside your CAG connection,

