- 6) The conserver will download a copy(ies) of the signed document(s) (see "Stand Alone eSig service SOP," section 3) to a study folder in VA network drive (i.e., R:\[name]) as study record. If necessary, the conserver can sign the ICF and save it back to this folder. The conserver will also place another copy(ies) of the signed document(s) in another study-specific folder (e.g. W:\) for HIMS to upload the documents into Electronic Health Record (EHR; i.e., VistA/CPRS or Cerner) (or other ways as agreed upon by local HIMS). The conserver should notify HIMS that the documents need to be placed in the EHR (per local agreement). The conserver will then check the EHR one week later to ensure the documents have been uploaded. If the documents have been uploaded, the conserver will remove the documents from the W:\ drive. If the documents have not been uploaded within one week, the conserver will re-notify HIMS to upload the documents into the EHR.
- 7) The conserver will document the consenting process as a "Research/Informed Consent" note in the subject's medical record (in CPRS). The note will specify that consent was obtained over phone/VVC/WebEx and DocuSign on the specific date. HIMS will attach the signed documents to this note.

Section 12.6 Decisional Capacity Assessment

12.6a) Describe the method(s) for determination of decisional capacity: (see ? for guidance) *Please note that documentation of the assessment is required.*

Participants must have decisional capacity for informed consent in order to meet eligibility for this study. To ensure this, the University of California San Diego Brief Assessment of Capacity to Consent (UBACC) will be used. The UBACC is a 10-item questionnaire tailored to specific study procedures. It queries participants about the basic procedures, risks, benefits, and purpose of the study, along with participant rights. Each item on the UBACC is scored on a 0 (incapable) to 2 (capable) scale. This will be administered at the time of obtaining informed consent.

The following are the questions and answers to this study's UBACC for card makers and recipients:

Card Makers:

1. What is the purpose of the study that was just described to you?
 - a. Response (2 = Study about Veterans making and receiving cards for suicide prevention and/or social connection)
2. What makes you want to consider participating in this study?
 - a. Response (2 = Increased social connection, help others, decreased suicide risk/behaviors)

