 - a. Response (2 = Increased social connectedness, decreased suicide risk and related behaviors).
9. Is it possible that being in this study will not have any benefit to you?
 - a. Response (2 = Yes)
10. Who will pay for your medical care if you are injured as a direct result of participating in this study?
 - a. Response (2 = VA San Diego)

12.6b) If subjects with limited decisional capacity will be enrolled, describe methods for obtaining subject assent or why they are not indicated:

Participants with limited decisional capacity will not be enrolled.

12.6c) If subjects with limited decisional capacity will be enrolled, describe procedures for respecting subject dissent and any additional safeguards or why these features are not needed:

Participants with limited decisional capacity will not be enrolled.

12.6d) If subjects with limited decisional capacity will be enrolled, describe the risk and, if greater than minimal, the relation to potential benefits:

Participants with limited decisional capacity will not be enrolled.

12.6e) If subjects with limited decisional capacity will be enrolled, describe the justification for the inclusion of any incompetent persons or persons with impaired decision-making capacity:

Participants with limited decisional capacity will not be enrolled.

Section 12.7 Consent by Legally Authorized Representative (Surrogate Consent)

12.7a) Where endorsed by the IRB, the following persons may be authorized to consent on behalf of persons who lack decision-making capacity in the indicated order of priority: (a) Health care agent (i.e., an individual named by the individual in a Durable Power of Attorney for Health Care (38 CFR.17.32(a)(iii)); (b) Legal guardian or special guardian; (c) Next of kin in this order: a close relative of the patient 18 years of age or older, in the following priority: spouse, child, parent, sibling, grandparent, or grandchild; (d) A close friend [however, California Health and Safety Code §24178 does NOT include the close friend category]

Agree Disagree

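### For a conserved Veteran who does not show decisional capacity on the UBACC, the protocol offers a conservator-consent enrolment route and also bars enrolment

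*Protocol*

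**What the plan says.** **The conservator route.** In the enrolment part of Section 9, if a Veteran is conserved, the coordinator is to obtain the conservator's "consent for study enrollment, as well as the assent of the conserved Veteran". Section 12.1d repeats the provision almost unchanged, ending "as well as the assent of the conservated Veteran".

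**The capacity criterion.** The inclusion list for card makers in Section 9 ends "3) access to transportation to attend the group, and (4) decisional capacity", and the list for card recipients ends "2) 18 years of age or older, and (3) decisional capacity". Sections 10 and 12.10a carry the same criteria. Section 9 specifies that this means capacity for informed consent, checked with the UBACC during consent. Section 12.6a states: "Participants must have decisional capacity for informed consent in order to meet eligibility for this study".

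**The answers on limited capacity.** Items 12.6b to 12.6e ask, for subjects with limited capacity, how assent is obtained, how dissent is respected and what safeguards apply, how risk relates to benefit, and why such persons are included. All four receive one answer: "Participants with limited decisional capacity will not be enrolled".

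**The surrogate terms.** Section 12.7a-d contains the form's standard statements on who may consent for someone lacking capacity, the representative's duties, the subject's right to refuse, and re-consent when capacity fluctuates.

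**The concern.** A surrogate's consent combined with the subject's assent is the usual arrangement for someone who cannot give informed consent. The form uses the terms that way: item 12.6b links assent to limited capacity, and Section 12.7a links surrogate consent to lack of capacity. Sections 9 and 12.1d therefore read as an enrolment route for people whom the inclusion criteria and Section 12.6 exclude.

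The main stake is protection. Participants have current or past high-risk flags for suicide. If someone without capacity entered by the conservator route, an inclusion criterion would be breached, and the study-specific details requested by 12.6b-e would be absent because the protocol says they are not needed.

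A lesser stake is measurement. Section 9 counts the proportions determined eligible and enrolled among its feasibility measures, and how such a Veteran is counted depends on which section staff apply.

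**Working it through.** The point concerns eligibility and consent text, and the protocol states no figure to reproduce. The check takes two conserved Veterans through the relevant sections.

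| Provision | Conserved, shows capacity on the UBACC | Conserved, does not show capacity |
|---|---|---|
| Sections 9, 10, 12.10a: inclusion criterion | Met | Not met |
| Section 12.6a: capacity required of participants | Met | Not met |
| Section 12.6b-e: limited capacity not enrolled | Not triggered | Enrolment barred |
| Section 12.1d: own consent obtained and capacity assessed for all prospective participants | Can be followed | Assessment done; no outcome stated for conserved Veterans |
| Sections 9 and 12.1d: conservator consents, Veteran assents | Can be followed as an added step | Route provided, with no capacity condition |

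In the first column every provision can be followed together. In the second, the last row points to enrolment and the first three to exclusion.

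Three further points bear on whether staff could settle such a case from the protocol:

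1. **Own consent and assent are not related to each other.** Section 12.1d has the Veteran's own consent obtained from all prospective participants, then separately provides for conservator consent plus assent. It does not say whether the second adds to the first or replaces it.
2. **No pass mark.** Section 12.6a describes ten UBACC items scored 0 to 2 but gives no score at which capacity is accepted.
3. **No conservator step in the remote procedures.** The WebEx and DocuSign steps in Section 12.1d provide for the subject's signature and none for a conservator.

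**Weight of one case.** The number of conserved Veterans is not given, so no total can be computed. With 80 planned participants (30 makers, 50 recipients), each such enrolment would be 1/80 = 1.25% of the sample: 1/30 = 3.3% of makers or 1/50 = 2.0% of recipients.

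**Link to the success criteria.** Aim 1 sets thresholds for group and meet-up attendance (70%), satisfaction (above 75%) and follow-up response (70%). It sets none for the proportions eligible or enrolled.

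**The case against.** The strongest reply is that the sections can be read in sequence. Section 12.1d assesses capacity for all prospective participants and makes no exception for conserved Veterans. Its WebEx steps run the UBACC first and go on to signature only once capacity is established. In Section 9 the capacity check also precedes the conservator sentence. On that reading the conservator's consent is a further step for Veterans who have already met the criterion.

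Much of this stands. A reader might infer that every conserved Veteran is both eligible and ineligible. The documents do not support that: nowhere do they equate being conserved with lacking capacity to consent to research, and a conserved Veteran who passes the UBACC meets every provision.

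A reader might also infer that the protocol has no terms at all on dissent or surrogate consent. That is wrong too, because Section 12.7 carries generic terms, including that no subject may be forced to take part against his or her will. What is missing is the study-specific content of 12.6b-e.

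The reply does not remove the narrower conflict. No sentence makes the conservator route conditional on passing the UBACC. If only Veterans with capacity were meant, one would expect them to consent rather than assent, and the answer to 12.6b treats an assent method as unnecessary. The Yes/No and Agree/Disagree marks in Sections 2.1c, 12h, 12i and 12.7 do not survive in the text available, so they cannot settle which reading was intended.

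**Conclusion.** The point holds, restricted to conserved Veterans who do not show decisional capacity on the UBACC. For them the protocol provides an enrolment route and prohibits enrolment, and the study-specific safeguards are left out because they are said not to be enrolled.

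The conclusion rests on the absence of any stated limit on the conservator route and on the form's own use of *assent* and of surrogate consent. It does not assume that conservatorship implies incapacity.

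Its size is unknown because the number of conserved Veterans is not given. A reader might infer that the feasibility conclusions are at risk. The documents do not support that, since no Aim 1 threshold depends on the eligible or enrolled proportions. The matter is one of consent and eligibility integrity in a population at high risk of suicide, and it should be corrected. The documents do not show which rule is intended.

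**What to change.** Reconcile the sections in one of two ways; the choice is the sponsor's.

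- **(a) Capacity required of everyone.** State in Sections 9 and 12.1d that the conservator's consent is additional to the capacity criterion and that a conserved Veteran who does not meet it on the UBACC is not enrolled. Align the word *assent* with that rule.
- **(b) Surrogate enrolment intended.** Amend the capacity criterion wherever it is listed (Sections 9, 10 and 12.10a) and Section 12.6a. Replace the four answers in 12.6b-e with the assent, dissent, risk and justification details those items request.

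Option (a) costs a few sentences in an amendment and possibly the loss of a few conserved Veterans. Option (b) takes more drafting because four items must be answered in substance.
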